Telehealth CBT to address social isolation in Veterans with chronic pain

Funding Agency: RR&D

Principal Investigator: [name]

Abstract

Loneliness—a subjective emotional state characterized by the perception of social isolation—is a psychosocial stressor that is associated with increased mortality and chronic pain. Individuals who have chronic pain and report loneliness experience greater pain-related interference in activities, depression, and suicidal ideation. Importantly, there are potentially effective interventions that can be used to decrease loneliness; however, there are no studies that have directly intervened on loneliness among Veterans with chronic pain. Cognitive-Behavioral Therapy for Loneliness (CBT-L) intervenes on loneliness by addressing negative beliefs that perpetuate loneliness, increase negative affect, and reduce one's ability to engage in social activities. For a Veteran with chronic pain, this is critical as addressing negative affect, and having a sense that one has social support and engages social support are key aspects of increasing functioning. While CBT for Chronic Pain (CBT-CP) comprises skills to promote social functioning, more robust efforts may be needed to better address lonely while also addressing functional impairment.

The proposed two-year study uses a novel application of a brief, phone-delivered, evidence-based intervention, CBT-L, to decrease loneliness by modifying socially-relevant maladaptive thinking patterns, increasing engagement in enjoyable and social activities, and improving problem solving skills. Participants will be recruited nationally using online advertising. The objectives of the current proposal are to adapt CBT-L to optimize its impact on Veterans with chronic pain, examine if the recruitment, retention, and treatment delivery is feasible and if CBT-L is acceptable to participants, and assess parameters of key outcomes among participants randomized to receive CBT-L versus CBT-CP to inform a subsequent larger clinical trial.

To achieve these objectives, we will adapt a manual through an evidence-based, iterative process then conduct one-arm trial of CBT-L (n=8) in Veterans with chronic pain reporting loneliness. After refining the manual and procedures following the one-arm trial, we will randomize a total of 40 participants to receive either CBT-L or CBT-CP. We will assess loneliness, the quality and quantity of social interactions, and pain outcomes such as pain-related interference, and pain catastrophizing at baseline and after the treatment period. We will also track participant flow, therapist adherence to the manual, participant homework completion and participant satisfaction with the treatment.

Contents

Study Protocol.....	4
Protocol Title: Telehealth CBT to address social isolation in Veterans with chronic pain	4
1.0 Study Personnel	4
2.0 Introduction	6
3.0 Objectives	6
4.0 Resources and Personnel	8
5.0 Study Procedures.....	8
5.1 Study Design	8
5.2 Recruitment Methods.....	10
5.3 Informed Consent Procedures	11
5.4 Inclusion/Exclusion Criteria.....	11
5.5 Study Evaluations.....	12
5.6 Schedule of Assessments	13
5.7 Data Analysis	14
5.8 Withdrawal of Subjects	15
6.0 Protection of Human Subjects	16
7.0 References.....	16

Study Protocol

Protocol Title: Telehealth CBT to address social isolation in Veterans with chronic pain

2.0 Introduction

Loneliness—a subjective emotional state characterized by the *perception* of social isolation¹—is a critical factor that has a significant public health impact. Loneliness is evident across the lifespan and can be experienced by anyone, although it occurs at higher rates among those with psychiatric disorders, people who are objectively isolated, and people with chronic illnesses.¹ Loneliness is characterized by a discrepancy in actual and desired social relationships. This discrepancy is what differentiates loneliness from objective social isolation (i.e., when people have few social contacts). Someone who is objectively socially isolated may not be lonely, and someone with many social contacts may be lonely.² A national study of adults ages 45+ found that over one-third reported loneliness.³ Among Veterans, 44% of a cohort of over 25,000 reported past-month loneliness,⁴ and over 70% of Veterans in primary care with probable major depression reported past-month loneliness.⁵ Loneliness increases the risk for a constellation of chronic diseases, and can lead to the development and exacerbation of psychiatric disorders and suicidal behavior.^{2,6} A meta-analysis of 70 studies found that loneliness increases odds of mortality by 29% after adjusting for key covariates.⁷

Loneliness is prominent and problematic in individuals experiencing chronic pain. Pain conditions affect over half the Veterans seen in the VHA,⁸ are leading causes of disability,⁹ have an estimated economic impact of over half a trillion dollars,¹⁰ and are associated with higher rates of psychiatric disorders, substance use, and suicide.^{8,11} Addressing loneliness in Veterans with chronic pain can have a profound impact on their psychosocial functioning and given its transdiagnostic nature, can impact comorbidities that are common among Veterans with chronic pain. Loneliness is highly prevalent among individuals with chronic pain, and pain is predictive of the onset of loneliness.¹² National survey data indicate that 40-50% of people with chronic pain report loneliness.^{13,14} Younger adults with chronic pain experience higher rates of loneliness, and often identify being more withdrawn, isolated, and having fewer friends relative to peers without chronic pain.^{15,16} The high rates of loneliness among people with chronic pain is extremely problematic. Social isolation and more social dysfunction predict longer duration of sick leave for people with low back pain.¹⁷ People with pain who are more socially withdrawn or isolated were twice as likely to report suicide ideation.¹⁸ Among nursing home patients with pain, loneliness is associated with lower life satisfaction, higher depression, less mobility, and lower ability to complete activities of daily living.¹⁹ Among both university student and community samples, loneliness is associated with depressive symptoms and pain-related interference in activities.^{20,21} Patients with pain who isolate also tend to over-identify with their pain and have lower levels of activity.²² Problems have been exacerbated by the COVID-19 pandemic, which has increased loneliness, exacerbated problems related to social resources, and reduced access to quality pain care.²³

Studies have sought to uncover key reasons why patients with chronic pain are lonely. Many indicate that pain negatively impacts socialization, and they do not feel understood by their social support network. Patients with chronic pain often feel like they have nothing in common with others and like they have few authentic and honest relationships.²⁴ Others report feeling “humiliated” and self-conscious about their difficulty engaging in activities, and that their

disability and negative mood prevent them from engaging in a broader range of activities.²⁵ Another study found that people with chronic pain want to avoid being self-pitied by others.²⁶ Some have separated themselves from other people because they “could not stand the laughter and happiness of others” making them feel more “miserable” and reluctant to start new relationships.²⁷ Researchers have also posited that pain catastrophizing (i.e., thinking the worst about pain) and fear avoidance behaviors in patients with pain can manifest themselves as social isolation.²⁸ Taken together, patients with pain experience significant suffering contributing to isolation and loneliness. This, in turn, contributes to behaviors that perpetuate loneliness because they are engaging in less activity and with fewer people who may lend support.

3.0 Objectives

The proposed study will provide critical feasibility and acceptability data on telehealth Cognitive-Behavioral Therapy for Loneliness and Pain (CBT-L/P) among Veterans with chronic pain who report loneliness. We will conduct a small single-arm trial ($n = 8$) for refinement of the intervention and study procedure. With the refined manual, Veterans with chronic pain reporting loneliness will be randomized to either CBT-L/P ($n = 20$) or CBT-CP ($n = 20$). The specific aims are as follows:

Aim 1: Refine the CBT-L/P manual by conducting a one-arm trial among Veterans with chronic pain reporting loneliness ($n = 8$). We will deliver CBT-L/P as part of a small, single-arm trial. This trial will allow us to collect feasibility of treatment delivery, and treatment satisfaction and acceptability data to further refine the manual.

Aim 2: Conduct a pilot randomized clinical trial to assess feasibility and acceptability among Veterans with chronic pain reporting loneliness. Participants will receive either CBT-L for Pain (n = 20) or CBT-CP (n = 20). We will assess: (1) treatment acceptability, (2) participant adherence to treatment, and (3) therapist fidelity. We will also assess outcome measure completion percentage, means and standard deviations, and level of correlation of repeated measurement of social functioning and pain outcomes.

4.0 Resources and Personnel

The study team consists of Drs. [name], [name], and [name], [name] (coordinator), [name] (coordinator), [name] (RA), [name] (RA), [name] (RA) and research therapists (TBD) to deliver the intervention. Research therapists will have at least a master's degree in a counseling/health-related field and prior CBT training Drs. [name], [name], and [name] will be in charge of executing the scientific objectives of this project. [name] will serve as project coordinator with additional assistance from [name]. The coordinators will assist in IRB documentation, participant payment and tracking, advertising, and conducting eligibility screening. The coordinators and research assistants will also complete screening and consent procedures, and complete assessment packets by telephone with participants at baseline, post-intervention and the 30-day follow-ups. Study therapists will deliver the study interventions.

5.0 Study Procedures

5.1 Study Design

Study sample: We will initially recruit 8 Veterans who screen positive for loneliness and have functional impairment from chronic pain to receive CBT-L. Once these 8 Veterans have completed study procedures, we will recruit an additional 40 to be randomized to either CBT-L/P or CBT-CP. This cohort will be randomized 1:1. The study will take place at the VA Center of Excellence for Suicide Prevention.

Screening: Research staff will screen by phone following a script. Potential participants will provide verbal consent to complete the screening measures. Those individuals meeting eligibility who are interested in participating will be scheduled for a phone-based consent and baseline assessment appointment. Based on our past experience, we expect approximately 25% of all participants who complete the screening to be eligible to and interested in participating. Therefore, we expect to screen no more than 600 participants to reach our sample of 48.

Assessments and Intervention:

Participants will be enrolled following consent and will complete the baseline assessment. Participants will schedule a convenient time for their telehealth-based intervention sessions. Post-treatment and 30-day post-treatment follow-up assessments will also be conducted by telehealth (phone, Teams, Webex, VVC), depending on the phase of the study. Participants will be paid \$40 each assessment completed. The post-treatment assessment will also include an exit interview for participants to describe acceptability of the intervention. Total compensation will be up to \$80 for the pilot phase, and \$120 for the randomized phase.

CBT for Loneliness and Chronic Pain (CBT-L/P):

The study team recently created a draft CBT-L manual (see **Appendix**) starting from a translation of the Kall et al. CBT-L manual as the base.³¹ We then incorporated relevant content and worksheets from the VHA Brief CBT manual into the CBT-L base.³² Pain-specific materials need to be integrated into the manual, which will be the focus during the refinement period.

The CBT-L adaptation for pain will use CBT-L strategies and account for impediments to functional improvement specific to Veterans with pain. Importantly, the approaches used will include those that anyone who is lonely might experience, but will also emphasize factors that are specific to people with chronic pain. To summarize some of the adaptations (see bulleted section below), participants will initially be presented with education on activating events that elicit thoughts, behaviors, and emotions that perpetuate loneliness, and in the case of chronic pain, continued impaired functioning related to pain. Sessions will then focus on identifying and changing unhelpful thoughts that contribute to loneliness. For example, if a participant states “I’m in so much pain that I’ll just yell at everyone if I leave my room,” or “It’s not worth doing anything because I annoy my family and I’m in too much pain,” they would be asked to estimate the accuracy of the thought and to dispute it. The original thoughts might be altered to “I could come out for a little bit and talk to people,” and “There are plenty of things that I can and have done and my family hasn’t been annoyed,” respectively. Assertiveness training will help reinforce effective strategies to improve communication with friends and family members to increase the likelihood of positive (or less aversive) social interactions and to communicate needs. Exposure and behavioral activation are used to approach feared behaviors (e.g., social interactions, especially those involving physical activity) and to increase the participant’s general activity level to improve mood. Loneliness contributes to avoidance thereby limiting use of adaptive coping strategies and reinforcing loneliness and negative affect. By increasing one’s activity level, particularly pleasant social activities involving physical activity, the participant’s mood may improve by decreasing avoidance, increasing the potential for social contact, reducing pain, and increasing self-efficacy to engage in activities. In the final sessions, the participant identifies barriers and ways to cope with loneliness-related problems by identifying strategies, evaluating the potential solutions, and selecting a plan to implement the strategies. This discussion will occur in the context of reducing pain flares, preventing a return to behavioral inactivation, and not allowing maladaptive thinking to drive poor coping, further maladaptive thinking, and lack of activity.

- **Session 1:** CBT Model & Goal Setting
 - Pain integrated into CBT model; goals also associated with addressing pain-related functional impairment
- **Session 2:** Identifying & Challenging Thoughts I
 - Pain-related thoughts perpetuating loneliness; loneliness-related thoughts perpetuating pain
- **Session 3:** Identifying & Challenging Thoughts II
 - Continued focus pain-related thoughts perpetuating loneliness; loneliness-related thoughts perpetuating pain
- **Session 4:** Assertiveness Training
 - Teaching effective communication and conflict resolution

- Session 5: Exposure & Behavioral Activation I
 - Incorporating physical activity into exposure and behavioral activation related to social activities
- Session 6: Exposure & Behavioral Activation II
 - Incorporating physical activity into exposure and behavioral activation related to social activities
- Session 7: Problem Solving
 - Problem solving issues around functional limitations, mobility, and other pain-related barriers
- Session 8: Review & Relapse Prevention
 - Review is specific to new content, using skills for CBT-L to address pain flares

CBT-CP: A Cochrane review indicated that CBT-CP reduces pain intensity, disability, mood outcomes, and pain catastrophizing.³³ CBT-CP is a nationally disseminated, evidence-based intervention with the goal of increasing functioning and quality of life through adaptive pain coping skills to support self-efficacy to manage pain.³⁴⁻³⁶ This is accomplished through pain psychoeducation, increasing activity level (e.g., walking, pleasant activities), and identifying and challenging pain catastrophizing. This CBT-CP protocol will be reduced from 10 to 8 sessions to match the number of sessions to CBT-L. The sleep hygiene session will be removed, and goal setting will occur in session 1 (rather than a stand-alone session). Both changes are consistent with Brief CBT-CP that was created in the VHA.³⁷ The manual is included as an **Appendix**.

Therapist training and fidelity. The investigators will provide training on CBT-L/P and CBT-CP. The training will begin with a training session provided, which will involve a review of basic CBT principles, rationale for using CBT-L/P and CBT-CP based on empirical support, and a detailed description of CBT-L/P and CBT-CP with the manual and handouts. Training will include didactics, guided readings as needed, role playing, and supervised training cases as needed until competency is met. We will monitor treatment fidelity by audio recording all CBT-L/P intervention sessions via Teams, Webex, VA Video Connect, or a FIPS-compliant recorder. Once coders are reliable, we will randomly code 30% of these sessions to be coded separately by two independent raters with 20% of these double coded. We will use the fidelity tool during the delivery of the intervention to continue monitoring adherence and competence to deliver the treatment materials. During the treatment delivery, feedback will be given weekly to the therapist during supervision sessions to ensure fidelity to the intervention protocol is maintained.

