5.7 Data Analysis

We will track rate of recruitment per week, and the percentage of participants who complete the protocol, and each follow-up. Participant treatment adherence will be assessed by tracking attendance and homework completion. Session-by-session participant feedback will be used to examine potential reasons for drop-out and non-adherence to inform our small RCT. Therapist adherence scores for the individual sessions and the overall interventions will be assessed as the percentage of the content delivered. Interrater reliability for fidelity will be assessed using intra-class correlation coefficients. We will assess the internal consistency of competence using Cronbach's alpha. Treatment acceptability will be assessed with the modified AARS and exit interview for a richer understanding. For participants who choose to withdraw prior to completing the full protocol, attempts will be made to conduct exit interviews to assess treatment experiences and reasons for early withdrawal. Interviews will be audio-recorded and transcribed. Interview data will be analyzed using matrix analysis,⁵⁴⁻⁵⁶ a systematic technique for data reduction to thematically organize and analyze data using rows, columns, and cells of a table. This process is time efficient, aligns well with results of in-depth analyses, allows for accurate summarizing of data, and facilitates participant comparisons.⁵⁵ Matrices are also an effective way to share findings with interdisciplinary team members for discussion.⁵⁴ Following the analyses, these matrices will be reviewed by the investigative team and expert panel in preparation for finalizing the intervention.

Consistent with descriptive analyses for pilot studies,⁵⁷ measure completion percentage and means and standard deviations for outcomes will be calculated at each assessment, including change scores and correlations across timepoints. We expect large standard errors

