Recruitment and informed consent procedures were designed to ensure patients do not feel like participation is required. Potential participants unable to understand the informed consent process will be excluded from participating. Screening interviews will be completed initially over the telephone (using a script) to assess eligibility criteria. Verbal consent will be obtained at this time to complete the screening. Participants screening positive for exclusion criteria will not be included in the study. For eligible and interested participants, a research coordinator will review the consent form and complete a brief questionnaire to ensure the potential participant understands the study. As with [name] other phone-based interventions, consent will be obtained verbally following the above outlined procedure. The participant will be mailed or emailed a copy for their records.

Participants will receive compensation for their participation in the study. The compensation amount will be based on the schedule that follows:

Baseline Assessment	\$40
Post-treatment Assessment	\$40
30-day Assessment (RCT only)	\$40

Therefore, the total compensation for completing all the study components would be \$120. Payments will be made following each study procedure listed above. Participants who do not complete the entire study for any reason, will receive compensation for the components that were completed per the above schedule of payments.

Protection Against Risk.

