As part of a standard practice, the PI will supervise the implementation of one audit regularly per year of the materials collected and produced as part of the study to ensure proper confidentiality and compliance with ethical principles, including informed consents, questionnaire data, and to make sure that the research staff are following established protocols. The PI will provide an annual summary report of all AEs to the IRB as part of the annual review. If no adverse events have occurred, the report will state, "No adverse events affecting human participants have occurred during this project year."

Data Monitoring. To ensure adequate participant recruitment and enrollment, each week, the PI will discuss the current number of participants contacted, screened, and enrolled from each site and compare those numbers to the expected based on our preliminary data. If after the first 4 months, it appears we are not reaching our expected number of participants, the PI will discuss potential barriers/obstacles and solutions. Discussions regarding recruitment and enrollment will continue at each meeting with study staff to ensure proper implementation of the study.

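### Does the 600-screen figure contradict the stated 25% screening yield?

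*Combined protocol and SAP*

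**What the plan says.** The Screening paragraph of section 5.1 gives a yield: "we expect approximately 25% of all participants who complete the screening to be eligible to and interested in participating". The next sentence draws a limit from it: "Therefore, we expect to screen no more than 600 participants to reach our sample of 48". The target of 48 (8 in the one-arm trial, 40 in the randomised trial) is the same in sections 5.1, 5.2 and 6.0.

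Enrolment comes later than a positive screen. Section 5.1 says "Those individuals meeting eligibility who are interested in participating will be scheduled for a phone-based consent and baseline assessment appointment", and section 6.0 adds "For eligible and interested participants, a research coordinator will review the consent form and complete a brief questionnaire". No loss rate is given for this step, nor for people who begin the screening measures and do not finish them.

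On the use of recruitment figures, the Abstract lists as an objective to "examine if the recruitment, retention, and treatment delivery is feasible" and says "We will also track participant flow". Section 5.7 says "We will track rate of recruitment per week, and the percentage of participants who complete the protocol, and each follow-up". Under Data Monitoring in section 6.0, the principal investigator reviews the numbers contacted, screened and enrolled each week and will "compare those numbers to the expected based on our preliminary data".

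**The concern.** The second sentence in section 5.1 is presented as a consequence of the first, and the arithmetic does not carry it. A reader who divides 48 by 25% gets 192, less than a third of 600. A reader who divides 48 by 600 gets 8%, less than a third of 25%.

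In a pilot that examines recruitment feasibility, this could matter in two ways. First, a final count well above 192 but below 600 might be called worse than expected on one reading and as expected on the other. Second, if the figures were carried forward, the larger trial's workload would differ by the same factor: per 100 enrolled, 100/0.25 = 400 screens against 100/0.08 = 1,250. Section 5.7 also does not list screening yield among the quantities to be summarised.

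**Working it through.** **Inputs.** Target 48, yield about 25% of completed screens, and upper limit 600, all from section 5.1. Loss rates are not in the documents; those used below are assumptions.

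**1. Attempt to reproduce 600.**
- Direct division: 48/0.25 = 192 (8/0.25 = 32 for the one-arm trial plus 40/0.25 = 160 for the randomised trial). Ratio 600/192 = 3.125.
- In reverse: 600 × 0.25 = 150 eligible and interested people; 48/600 = 8.0%.
- Eligibility and interest as two separate 25% steps: 48/(0.25 × 0.25) = 768.

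None of these gives 600.

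**2. Can chance explain the margin?** The number of screens up to the 48th enrolment is negative binomial, with mean 48/p and SD √(48(1 − p))/p. At p = 0.25 the mean is 192, the SD is √36/0.25 = 24.0, and the 95% range is 148 to 242. For a 99.9% chance of reaching 48, 276 screens are enough. Chance alone does not explain 600.

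**3. Can loss outside the 25% explain it?** The overall yield is (share who finish screening) × 0.25 × (share of positive screens who enrol).

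| Assumed overall yield | How it could arise | Mean screens | 95% range | P(48 reached within 600) |
|---|---|---|---|---|
| 25% | no loss | 192 | 148 to 242 | essentially 1 |
| 20% | 20% loss | 240 | 184 to 305 | above 0.999 |
| 12.5% | 50% loss | 384 | 290 to 493 | 0.9998 |
| 10% | 60% loss | 480 | 360 to 618 | 0.959 |
| 8% | 68% loss | 600 | 449 to 774 | 0.522 |

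The loss column is the combined loss over both steps. For 600 to be the mean count, the two shares must multiply to 0.08/0.25 = 0.32. They could do so at 57% each: 0.57 × 0.25 × 0.57 = 8.1%, and 48/0.0812 = 591. Nothing shows that the team meant this. It does show that 600 and 25% can stand together without an extreme loss at either single step.

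**4. Is there a sharp line between as expected and below expectation?** Against 25% with no loss, counts above 242 fall outside the 95% range. With an assumed 20% loss, the probability of exceeding 242 is about 45%. The yield is itself approximate and rests on past experience, while recruitment runs through advertising, mailed letters, provider referral and other studies (section 5.2). Neither 192 nor 242 is a firm benchmark.

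**5. What depends on 600?** The 48 is fixed separately. Section 5.7 is descriptive and uses neither 25% nor 600. The weekly comparison in section 6.0 is with preliminary data that the documents do not print. Its 4-month check leads only to a discussion of obstacles and solutions. No progression criterion or stopping rule refers to either figure.

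**The case for a change.** The strongest case for a change is that the sentence states an expectation and derives it from 25%, so a margin of more than three should be explained. A limit that would be met with 96% probability at a true yield of only 10% is no test of the 25% assumption. Section 5.1 is also the only place where a screening expectation is printed, and section 5.7 does not name yield. The correction would cost a sentence or two and use counts already collected.

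Much of this stands. The derivation is a non-sequitur, and 600 is too generous to serve as a recruitment benchmark. What does not stand is the consequence. The plan does not use 600 as a benchmark. The counts needed for the yield are tracked as participant flow and in the weekly review, so leaving yield out of section 5.7 is a matter of where it is listed. A confidence interval needs nothing beyond those counts: for example, 48/192 gives 25.0% (Wilson 95% CI 19.4% to 31.6%) and 48/600 gives 8.0% (6.1% to 10.5%). The larger trial would be planned from that observed yield, so the contrast of 400 with 1,250 screens would not arise. Printing 192 with its no-loss range in place of 600 would also swap an unexplained margin for none.

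**Conclusion.** The concern does not call for a change. The 600 does not follow from 25%: the count implied by that yield is 192, and 600 corresponds to 8%. But it is an upper limit with an unexplained margin, and 192 lies within it. The gap is clerical. It alters no sample size, visit, analysis or conclusion, and the observed yield will replace both figures.

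This rests on three readings: that 600 is a maximum, as its wording indicates; that the 25% base is completed screens only; and that the flow and weekly counts are kept as the Abstract and section 6.0 say. If the team edits section 5.1 for another reason, it could call 600 an administrative maximum or state the allowance for unfinished screens and loss before consent. That would help the reader and change nothing that the trial does.

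### The random 30% fidelity sample has no stated stratification by session number, so coverage of the eight CBT-L/P sessions is left to chance (minor)

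*Combined protocol and SAP*

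**What the plan says.** The combined protocol and SAP, section 5.1 (Therapist training and fidelity), sets the sampling frame: "We will monitor treatment fidelity by audio recording all CBT-L/P intervention sessions". From these, "we will randomly code 30% of these sessions to be coded separately by two independent raters", "with 20% of these double coded". No stratification by session number, therapist or phase is mentioned, and no minimum count per session number.

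Section 5.7 sets the reporting level: "Therapist adherence scores for the individual sessions and the overall interventions will be assessed as the percentage of the content delivered". It does not say how the overall score is formed from the coded recordings.

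The session outline in section 5.1 lists eight CBT-L/P sessions with largely different content, from the CBT model and goal setting through assertiveness, exposure and problem solving to relapse prevention. Section 3.0 plans 8 participants in the one-arm trial and 20 in the CBT-L/P arm of the RCT, and names therapist fidelity among the Aim 2 assessments. Section 5.7 will look into reasons for drop-out but gives no expected rate.

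**The concern.** A session-level adherence score shows which parts of a newly adapted manual therapists deliver as intended. That is useful before a larger trial. Because content differs by session, a recording of session 2 says little about delivery of session 7. A draw that ignores session number leaves the count behind each score to chance. One session could be judged on two recordings and another on ten, without anyone having chosen this. In the small one-arm phase, whose purpose is to refine the manual, a session could have no coded recording at all.

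**Working it through.** **Inputs.** Eight sessions per participant (5.1); 20 RCT and 8 one-arm CBT-L/P participants (3.0); 30% coded (5.1). The plan gives percentages but no count of coded sessions, so there is no stated figure to reproduce. Counts below are of distinct coded recordings, so the double-coding clause does not alter them. Attendance is assumed complete unless stated.

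**1. One session number, RCT arm.** Recordings: N = 20 × 8 = 160. Coded: n = 0.30 × 160 = 48. Recordings of a given session number: K = 20. Under a simple random draw the coded count is hypergeometric.
- Mean = nK/N = 48 × 20/160 = 6.
- Variance = n(K/N)(1 − K/N)(N − n)/(N − 1) = 48 × 0.125 × 0.875 × 112/159 = 3.70, so SD = 1.92.
- The 2.5% and 97.5% points are 2 and 10.
- P(3 or fewer) = 9%.

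**2. Lowest count over the eight session numbers** (multivariate hypergeometric).

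| Frame | Recordings | Coded | Mean per session number | P(some session number ≤ 3) | P(some ≤ 2) |
|---|---|---|---|---|---|
| RCT arm | 160 | 48 | 6.0 | 60% | 21% |
| Both phases pooled | 28 × 8 = 224 | 67 | 8.4 | 9% | 2% |

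For the one-arm phase alone there are 8 × 8 = 64 recordings and 19 coded, so the mean is 19/8 = 2.4. A given session number has no coded recording with probability 5%; at least one of the eight has none with probability 35%.

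**3. Drop-out (assumed, RCT arm).** Two illustrative attendance patterns over sessions 1 to 8:
- 20, 19, 18, 17, 16, 15, 14, 14: 133 recordings, 40 coded. Session 8 expects 40 × 14/133 = 4.2, and P(3 or fewer) is 34%. Sessions 1–4 supply 74/133 = 56%.
- 20, 18, 17, 15, 14, 13, 12, 12: 121 recordings, 36 coded. Session 8 expects 36 × 12/121 = 3.6, and P(3 or fewer) is 50%. Sessions 1–4 supply 70/121 = 58%.

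Across assumed losses of 0% to 50% by session 8, the share from sessions 1–4 runs from 50% to 60%.

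**4. Effect on an overall score, if recordings are pooled.** Assume adherence of 90% in sessions 1–4 and 70% in sessions 5–8. The pooled score is 70 + 20 × share: 81.1 at 56% (using 74/133) and 81.6 at 58% (using 70/121), against 80.0 with equal weights. The shift is 1 to 2 points.

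**5. What stratifying gains.** With exactly 6 per session number, the variance of a session mean is proportional to 1/6. With a random count it is proportional to E[1/n], where n is now that session number's coded count (taken as at least 1). In the RCT arm 6 × E[1/n] = 1.144, so the standard error is √1.144 = 1.07 times as large. Stratifying therefore trims it by about 7%, or about 9% with a finite-population correction for 20 recordings. Proportional stratification removes only the chance imbalance: at 12 attendees session 8 still gets about 0.30 × 12 = 3.6.

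**The case against.** The other side has substance.

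- **The text can be read without conflict.** Scores for individual sessions may mean one score per coded recording, which a random 30% supports fully. Section 5.1 is silent on strata rather than ruling them out. This stands, so the point is conditional on reading the phrase as session numbers.
- **The frame is open.** Section 5.1 does not confine recording to the RCT, and pooling the phases makes thin coverage unlikely (9% and 2%). This also stands. However, the manual is refined between phases, so pooling would mix two versions, and the plan does not say that it will pool.
- **60% is a worst-of-eight figure.** For a named session number the chance of 3 or fewer is 9%. About 6 recordings is few in any case, which follows from having 20 participants rather than from the draw. Stratifying improves precision only slightly.
- **There are safeguards.** All CBT-L/P sessions are recorded, so a thin session could be topped up, and the fidelity tool is also used during delivery with weekly supervision. These reduce the consequences but do not assure coverage in the coded sample.

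A reader might go further and infer that later sessions will be thinly coded and that the overall score will mainly reflect early content. The documents do not support this. They give no attrition rate; at full attendance sessions 1–4 supply exactly half the sample; and under the losses assumed above they supply 56% to 58%. Nor does section 5.7 say that the overall score pools recordings. A simple random sample estimates adherence in treatment as delivered without bias. Equal weight per session number answers a different question, which the plan neither adopts nor excludes.

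**Conclusion.** The point holds as a minor design improvement. No stratification is stated for the fidelity draw, although session-level adherence is to be reported for sessions of differing content. In the RCT arm at full attendance, chance alone gives a range of 2 to 10 coded recordings around a mean of 6. This rests on three assumptions: individual sessions means session numbers, the draw is a simple random one, and the RCT arm is sampled on its own. It needs no drop-out. Thinner coverage of later sessions is possible but cannot be sized from the documents. The analysis is descriptive and no progression rule depends on these scores, so the consequence is limited to how evenly and reliably the session scores are supported.

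**What to change.** In section 5.1, state that the same 30% will be drawn at random within session number, separately in each phase, and spread over therapists where possible. At full attendance this gives 6 recordings for each session number in the RCT arm (8 × 6 = 48). In the one-arm phase it gives 2 or 3 each (for example 5 × 2 + 3 × 3 = 19).

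In section 5.7, state that session-level scores are by session number, give the number of recordings behind each, and say how the overall score is formed. Optionally, report the equal-weight mean of the eight session scores beside the pooled score, so that any effect of uneven attendance is visible.

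The cost is a sentence or two in each section and no added coding load. The pooled overall score remains an unbiased estimate of adherence as delivered, apart from rounding within strata. The gain is assured coverage of every session and a small improvement in precision. It does not offset thinning caused by drop-out.
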